9.3 POPULATIONS FOR ANALYSES

The following datasets will be considered in study analyses:

- Intention-to-treat analysis dataset will include all subjects that receive assignment and will be analyzed according to the initial randomization assignment.
- Modified intention-to-treat (MITT) analysis dataset will include all randomized subjects that receive the study intervention and will be analyzed according to the initial randomization assignment.
- Per-protocol analysis dataset will include all randomized subjects that receive the study intervention consistent with the initial randomization assignment and complete the scheduled visits and will be analyzed according to the initial randomization assignment. In cases where subjects receive an intervention other than the one randomly assigned, an as-treated analysis will additionally be performed according to the actual intervention received.

9.3.1 Evaluable for Toxicity

All subjects will be evaluable for toxicity from the time of their study agent administration.

9.3.2 Evaluable for Objective Response

Not applicable.

9.3.3 Evaluable Non-Target Disease Response

Not applicable.

9.4 STATISTICAL ANALYSES

9.4.1 General Approach

In general, descriptive statistics will be tabulated by treatment arm for endpoints of interest. This will include point estimates (mean, geometric mean, median, or proportions) and their respective 95% confidence intervals. Formal comparisons will use standard methods, contingency tables for categorical variables, t-tests for comparing means if data (or log-transformed data) follow a normal distribution (log transformation or not depends on which method is closer to normality), or nonparametric analogs for comparing medians if otherwise. Unless specified in the subsequent sections, comparisons will be two-sided with type I error rate of 0.05.

Missing data will be considered as “missing completely at random” provided missing data is modest (e.g., <10%). We will examine the “missing completely at random” assumption if missing data is more than 10%. If the assumption does not hold, missing data will be handled under the “missing at random” assumption (that is, missingness depends only on observed variables) via methods such as multiple imputation and inverse propensity weighting. To handle the possibility of “missing not at random,” a sensitivity analysis will be performed by imputing missing binary observations with the observed proportion in the opposite arm. A secondary sensitivity analysis will be considered by imputing missing binary observations as failures.

Randomization: Randomization will be 3:1 allocation to L9LS 900 mg and placebo arm stratified by sex (2:1 female to male ratio) and weight (1:1:1 to three weight groups). To limit the number of dropouts before administration of study agent, randomization and administration will occur as close in time as possible.

9.4.2 Analysis of the Primary Endpoints

Analysis for the primary endpoint for safety and tolerability is described in section [9.4.5](#).

Analysis for the primary efficacy endpoint, protective efficacy with Pf infection determined by blood smear, is described in section [9.4.4](#).

9.4.3 Analysis of the Secondary Endpoints

Analysis of the secondary efficacy endpoint, with Pf infection determined by RT-PCR, is described in section [9.4.4](#).

Analyses of the secondary endpoints related to PK and the association of monoclonal antibody concentration with Pf infection risk are described in section [9.4.6](#).

9.4.4 Efficacy Analyses

Incidence of malaria infection is primarily defined as blood smear–positive Pf infection through 24 weeks after administration, and secondarily as determined by RT-PCR. The efficacy analyses will be MITT.

The primary efficacy analysis will be based on time to the first infection. The survival patterns will be described by Kaplan-Meier curves for each arm. The protective efficacy of the study product will be assessed from the Cox proportional hazards model with study arm as the only regressor and estimated by one minus the hazard ratio. This will be achieved via R package “straweib” that accounts for interval censoring. To address the heterogeneity of the study population, as a sensitivity analysis, a Cox regression with regressors other than the study arm will be additionally performed to account for potential differences among participants. The regressors will include time of enrollment and possibly those covariates that are significantly different between the study product arm and the placebo arm in spite of randomization.

The secondary efficacy analysis will be based on the proportion of subjects who become infected during the 24-week follow-up period. The proportion of subjects who become infected during the 24-week follow-up period will be estimated for each arm and compared across arms based on Kaplan-Meier estimates along with 95% confidence intervals via R package “bpcp.” This estimation accounts for right censoring and the comparison should be equivalent to Fisher’s exact test in case of no censoring. Though not accounting for interval censoring, the Kaplan-Meier estimates are appropriate as the interest is on infection at 24 weeks only.

Protective efficacy of L9LS will be primarily assessed over all participants by comparing all L9LS recipients with placebo recipients. As a secondary objective, the protective efficacy of L9LS will also be assessed among female participants by comparing female recipients of L9LS with female placebo recipients; and a stratified analysis by weight will also be performed. An exploratory analysis will be conducted to assess how the weight-based dosage, in terms of mg of L9LS per kg of subject body weight, affects the protective efficacy. No multiplicity adjustment will be applied to the secondary and exploratory analyses.

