
1. To evaluate the relationship between weight-based dosing of L9LS at 900 mg administered SC and protection against naturally occurring Pf infection in healthy Malian adults during a single malaria season as detected by blood smears and RT-PCR.
 
2. To determine whether ADA to L9LS can be detected in sera of recipients at specific timepoints throughout the study.
 
3. To assess for IgG1 allotypes and allotype-specific effects on L9LS PK.
 
4. To explore and characterize the cellular immune response to L9LS.
 
5. To determine if the efficacy of L9LS is specific to certain Pf parasite genotypes at the CSP locus.
 
6. To explore the impact of pre-existing parasitemia on the protective efficacy and PK of L9LS.
 
7. To explore the impact of pre-existing CSP antibodies on the protective efficacy and PK of L9LS.
	
1. Pf blood-stage infection as detected by microscopic examination of thick blood smear and RT-PCR for 24 weeks after administration of study agent
 
2. Measurement of ADA to L9LS in sera of recipients.
 
3. Assessment of IgG1 allotypes and allotype-specific effects on L9LS PK.
 
4. Characterization of the cellular immune response to L9LS.
 
5. CSP genotyping of parasites isolated from study subjects.
 
6. Pre-existing parasitemia detected by microscopic examination of thick blood smears or RT-PCR before L9LS administration.
 
7. Pre-existing CSP-specific antibodies measured in sera collected before L9LS administration.
	
1. Blood smear is the gold standard for diagnosis of blood-stage Pf infection and RT-PCR is more sensitive than blood smear for detecting Pf blood-stage infection.
 
2. ADA to L9LS may impact the PK and activity of L9LS.
 
3. Subject IgG1 allotype may impact the PK and activity of L9LS.
 
4. L9LS-induced cellular immune responses may be associated with Pf infection risk.
 
5. L9LS efficacy may be specific to certain Pf parasite genotypes at the CSP locus.
 
6. Pre-existing parasitemia may impact the protective efficacy and PK of L9LS.
 
7. Pre-existing CSP-specific antibodies may impact the protective efficacy and PK of L9LS.

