4.4 JUSTIFICATION FOR SEX AND WEIGHT STRATIFICATION

Weight stratification is employed in this protocol to approximate an even distribution of weight-based (mg/kg) dosing of L9LS, which will be administered at a single fixed dose of 900 mg. Sex stratification at a female to male ratio of 2:1 is employed in this protocol to obtain robust data on L9LS safety, PK, and efficacy among women of child-bearing potential in preparation for a phase 1 trial of L9LS in pregnant women—a high-priority clinical-use case for anti-malarial MAbs. Data on adult males could inform future studies of migrant workers who are intermittently exposed to malaria, as well as elimination trials that target all sexes and age groups.

For weight stratification, the female weight distribution was divided into 3 strata based on the 33.3% and 66.6% quantiles: 45.0 – 54.9 kg (low), 55.0 – 63.9 kg (medium), and 64.0 – 90.0 kg (high), thus yielding weight-based dosing strata of 16.7 – 20 mg/kg, 14.3 – 16.4 mg/kg, and 10 – 14.1 mg/kg, respectively. Similarly, the male weight distribution was divided into 3 strata based

on the 33.3% and 66.6% quantiles: 50.0 – 61.9 kg (low), 62.0 – 72.9 kg (medium), and 73.0 – 100.0 kg (high), thus yielding weight-based dosing strata of 14.8 – 18 mg/kg, 12.5 – 14.5 mg/kg, and 9 – 12.3 mg/kg, respectively. For females, there will be 64 (i.e., 192/3) participants in each of the 3 weight strata; however, to minimize barriers to eligibility and enrollment, the required minimum number of participants in each weight strata is 40, beyond which any participant within the eligible weight range (45.0 – 90.0 kg) can be enrolled. For males, there will be 32 (i.e., 96/3) participants in each of the 3 weight strata; however, to minimize barriers to eligibility and enrollment, the required minimum number of participants in each weight strata is 20, beyond which any participant within the eligible weight range (50.0 – 100.0 kg) can be enrolled.

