8 STUDY ASSESSMENTS AND PROCEDURES

8.1 SCREENING PROCEDURES

Screening will be performed at all study sites. The study staff will explain the study to the prospective subject, complete the study comprehension examination and obtain consent (section [10.1](#)), and assess eligibility. Consent will be obtained before any study-related procedures are performed.

The following screening procedures and evaluations must be performed within -56 to -7 days of study intervention. Screening may take place over multiple visits if necessary.

- Confirmation of identity, age, and residency.

- Complete review of medical history and medication use.
- Complete physical examination, including height and weight.
- Vital signs (temperature, blood pressure, and pulse).
- 12-lead ECG.
- Urine collection for urinalysis (urine dipstick or formal urinalysis; acceptable laboratory parameters defined in [Appendix A](#)).
- For women, serum β -hCG pregnancy test.
- Blood collection via venipuncture for screening evaluations:
 - HIV tests: 2 rapid diagnostic tests (RDTs), plus ELISA if the RDTs are discordant. A subject will be referred for medical care for 2 positive RDTs or a positive ELISA. If the ELISA is negative, no further work-up will be done. Pre- and post-test HIV counseling will be provided.
 - HBV ELISA and HCV ELISA (PCR, if indicated) tests. If either test is positive, the subject will be referred for care regardless of the ALT result.
 - Hemoglobin typing sample will be stored at screening, and hemoglobin typing will be performed if the subject is enrolled; this test will not be used in eligibility assessments.
 - Complete blood count (CBC) with differential.
 - ALT.
 - Cr.
- Pregnancy prevention confirmation and counseling.

A prospective subject who has any clinically significant abnormal finding and/or is diagnosed with a medical condition at screening or during the conduct of the study will be notified and referred for medical care. Per national requirements for reporting communicable diseases, confirmed positive test results for HIV, HBV, and HCV will be reported to the local health department according to applicable laws and appropriate medical referrals initiated. The cost of initial and long-term treatment and care of medical conditions diagnosed during the screening process will not be reimbursed by the study but referrals to relevant specialist will be provided.

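### The randomization strata (sex and weight group) are left out of the primary efficacy model, and the sensitivity model's covariate rule would not bring them back in

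*Combined protocol and SAP*

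**What the plan says.** Section 9.4.1 sets a 3:1 randomization "stratified by sex (2:1 female to male ratio) and weight (1:1:1 to three weight groups". Section 4.4 defines the weight bands separately for females and males, which makes six strata. The planned sizes are 64 in each female band and 32 in each male band. These may vary: for females, "the required minimum number of participants in each weight strata is 40", and the male minimum is 20.

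Section 9.4.4 assesses protective efficacy as one minus the hazard ratio from a "Cox proportional hazards model with study arm as the only regressor", allowing for interval censoring. Sex and weight appear in the efficacy analysis in three places only:

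- the secondary comparison among females;
- the secondary statement that "a stratified analysis by weight will also be performed";
- the exploratory analysis of mg/kg dose.

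The one adjusted version of the primary comparison is a sensitivity model. Its regressors are time of enrollment and "possibly those covariates that are significantly different between the study product arm and the placebo arm in spite of randomization". The documents give no reason for leaving the strata out of the primary model, and no candidate list for the sensitivity model.

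**The concern.** There are two linked points.

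First, stratified allocation makes the arms more alike on sex and weight than simple randomization would. If those factors predict infection, the true sampling variation of the arm comparison shrinks, but the arm-only model's standard error does not reflect this. The test then rejects too rarely under the null. The hazard ratio also moves toward 1, because the marginal hazard ratio over a mixed population differs from the within-stratum one.

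Second, section 9.4.4 says the sensitivity model is there to address heterogeneity of the study population, but its selection rule cannot do that well. Under randomization, a significant baseline difference between arms is a chance event and says nothing about whether the covariate predicts infection. Factors balanced by design will not be flagged, so the adjusted model passes over the two factors the design controls. Its other covariates cannot be known until treatment codes are available.

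At stake are some efficiency and the value of the robustness check. Validity of the primary test is not at stake.

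**Working it through.** **Inputs from the documents.** 216 L9LS and 72 placebo (section 6.1.2, Table 1); stratum sizes 64 × 3 and 32 × 3 (section 4.4); two-sided 0.05 (section 9.4.1); 10% dropout, placebo infection of 0.5, and 78.2% in the earlier trial (section 9.2.2).

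**Assumed, because the documents give no figure.** The effect of sex and weight group on infection. The log-hazard step between adjacent weight groups was set at 0, 0.1, 0.2, 0.3 and 0.5. Heavy versus light this is exp(2 × step) = 1.0, 1.2, 1.5, 1.8 and 2.7.

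**Step 1: the plan's own figure.** Table 4 gives 93% for 72 per arm, placebo rate 0.5 and efficacy 0.6, where efficacy is one minus the ratio of infection rates.

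- L9LS rate = 0.5 × (1 − 0.6) = 0.2
- Hazard ratio = ln(0.8)/ln(0.5) = 0.322
- Events = 0.9 × 72 × (0.5 + 0.2) = 45.4
- Freedman: z = √45.4 × (1 − 0.322)/(1 + 0.322) − 1.96 = 1.50, power 93%

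All 27 cells of Table 4 reproduce within 2 points. The calculation makes no allowance for strata. From here on, efficacy means one minus the hazard ratio, as in section 9.4.4.

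**Step 2: the arm-only estimate.** An arm-only interval-censored Weibull model was fitted in large samples to six exponential strata (weights 2/9 × 3 and 1/9 × 3), with smear visits from day 7 to day 168, 3:1 allocation, no sex effect and true within-stratum efficacy of 60%.

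| Heavy v light hazard ratio | 1.0 | 1.2 | 1.5 | 1.8 | 2.7 |
|---|---|---|---|---|---|
| Arm-only efficacy, placebo infection 78.2% | 60.0% | 59.9% | 59.6% | 59.1% | 57.6% |
| Arm-only efficacy, placebo infection 50% | 60.0% | 60.0% | 59.8% | 59.6% | 58.8% |

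The largest shifts are 60.0 − 57.6 = 2.4 points and 60.0 − 58.8 = 1.2 points.

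**Step 3: type I error.** 10,000 null trials per setting at 78.2% placebo infection, Wald test. The sex log-hazard was varied too (0, 0.1, 0.2, 0.3, 0 across the columns), so this is not a weight-only series.

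| Heavy v light hazard ratio | 1.0 | 1.2 | 1.5 | 1.8 | 2.7 |
|---|---|---|---|---|---|
| Arm-only | 5.2% | 4.9% | 4.7% | 4.5% | 4.0% |
| Adjusted for sex and weight group | 5.5% | 5.2% | 5.1% | 5.0% | 5.3% |

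Monte Carlo error is about 0.2 points. At 50% placebo infection, with weight step and sex effect both 0.3, the figures are 4.0% arm-only and 4.5% adjusted.

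**Step 4: power.** 4,000 trials per setting, weight step 0.3, sex effect 0.3 (none in the female analysis).

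| Setting | Arm-only | Adjusted |
|---|---|---|
| Placebo 50%, efficacy 60% | 97.9% | 98.1% |
| Placebo 78.2%, efficacy 60% | 99.9% | 100% |
| Placebo 78.2%, efficacy 30% | 57.3% | 60.7% |
| Females (144 v 48), placebo 50%, efficacy 60% | 91.0% | 91.4% |

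A hand check of the first arm-only figure, ignoring strata: L9LS rate = 1 − 0.5^0.4 = 0.242; events = 0.9 × 216 × 0.242 = 47.1 and 0.9 × 72 × 0.5 = 32.4; standard error = √(1/47.1 + 1/32.4) = 0.228; z = −ln(0.4)/0.228 − 1.96 = 2.05, power 98%.

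**Step 5: stronger assumed effects.** A separate simulation (2,000 trials per setting, exact event times, Cox model stratified by the six strata) used hazard ratios of 1, 1.5, 2 and 3 both for sex and per weight step, at 78.2% placebo infection.

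| Hazard ratio, sex and per weight step | 1 | 1.5 | 2 | 3 |
|---|---|---|---|---|
| Type I error, arm-only | 5.0% | 3.0% | 2.5% | 1.4% |
| Type I error, stratified | 5.1% | 4.1% | 5.3% | 5.9% |
| Efficacy estimate, arm-only (true 60%) | 60% | 58% | 54% | 47% |

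The stratified estimate stayed at 60% throughout, and power at 60% efficacy was at least 99% for both models. The direction agrees with steps 2 and 3; the larger shifts come from the larger assumed effects.

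**Step 6: the selection rule.** In 20,000 allocations with permuted blocks of 4 (assumed, as no block size is stated) and stratum sizes varied above the minima, chi-square tests of sex and weight group by arm were never significant. The smallest p-values were 0.63 and 0.88. A second check with 2% random exclusions found 0 of 4,000 for sex, weight group and continuous weight, against about 5% for each under unstratified randomization.

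**The case against.** The strongest reply is that this changes almost nothing. Power at the planned efficacy is essentially the same, the estimate moves by at most 2.4 points, and that needs a 2.7-fold hazard between weight groups. Table 4 plans for efficacy of 0.6 to 0.8, so the gain at 30% lies outside the planned range. All this stands, and it limits the point to efficiency and prespecification.

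Nor do the documents say that sex or weight predicts infection. Section 4.4 gives other reasons for the strata: an even spread of mg/kg dose, and good data in women of child-bearing potential. If weight acts only through dose, it modifies the effect within the L9LS arm, and a main-effect term does not model that. In simulations with weight-specific hazard ratios of 0.3, 0.4 and 0.5 and no baseline effect (300 trials per setting), median efficacy was 59.7% with either model at 78.2% placebo infection, and 58.9% arm-only against 59.4% adjusted at 50%. With hazard ratios of 0.55, 0.70 and 0.85 (400 trials), power was 61% against 59%. This also stands: in that case adjustment gains nothing material, but it costs nothing material either.

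The shift in the hazard ratio is a change of target from marginal to conditional, and is not a bias. That is correct, and is why the arm-only estimate should still be reported. Full stratification would also leave thin male cells: 32/4 = 8 placebo recipients each as planned, and 20/4 = 5 at the minimum. That favors model terms over six separate strata.

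Finally, time of enrollment is fixed in advance, so only the optional covariates are open. True, but those are the ones that the significance rule governs, and the rule still cannot reach the strata.

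**Conclusion.** The concern holds as a recommended improvement and does not affect validity. The randomization factors are absent from the primary model, and the baseline-significance rule would in practice never select them. If neither factor predicts infection, nothing is lost. If they do, the arm-only test is conservative and its estimate lies below the within-stratum value: by 0 to 2.4 points at 78.2% placebo infection, and 0 to 1.2 points at 50%, for heavy-versus-light hazard ratios of 1.0 to 2.7. Larger shifts need much stronger effects. Power is barely affected at the planned efficacy; a gain of 60.7 − 57.3 = 3.4 points appears at 30% efficacy.

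These sizes rest on assumed prognostic effects, exponential infection times and 10% dropout. The selection result assumes that the stratified lists work as planned. Confidence is medium, because the prognostic strength of sex and weight is not documented. The clearer weakness is the sensitivity model: its covariates are not fixed before unblinding and would leave out the design factors.

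**What to change.** In section 9.4.4:

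1. Fit the primary interval-censored model with study arm, sex and weight group as prespecified terms, or stratify by them. Define weight group within sex, since the bands in section 4.4 differ. Do the same for the RT-PCR endpoint, and use weight group in the female analysis.
2. Keep the arm-only model as a reported sensitivity analysis, and state that the adjusted hazard ratio is conditional on stratum while the arm-only one describes all participants.
3. Replace the significance rule with a list fixed before unblinding, in addition to the strata: time of enrollment, village of residence, age and pre-dose Pf status. The documents cite no evidence that these predict infection, so the sponsor may choose otherwise. What matters is that the list is fixed and the strata are in the model.

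No new data are needed. Screening includes "Confirmation of identity, age, and residency", and section 3 already lists "Pre-existing parasitemia detected by microscopic examination of thick blood smears or RT-PCR before L9LS administration" as an exploratory endpoint. The cost is two sentences of text and three model parameters (one for sex, two for weight group). Simulated type I error of the adjusted model is 5.0% to 5.5% at 78.2% placebo infection. The one real change is from a marginal to a conditional hazard ratio, which item 2 covers.

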9.4.5 Safety Analyses

Safety analysis will be primarily MITT where individuals who receive assignment but do not receive any product are excluded. Because of blinding and the brief length of time between assignment and administration, such cases will be very few.

Safety data will be presented by line listing and tables at the individual level to provide details on safety events such as severity, duration, and relationship to study product. The number and percentage of subjects with 1 or more AEs will be summarized by dose arm along with the exact 95% confidence intervals of the AE rate. For subjects experiencing more than 1 AE, the subjects will be counted once under the event of highest severity.

In the efficacy study, comparisons between the dose arms and the control arm will be additionally performed in terms of the proportions of solicited AEs, related AEs, and SAEs.

In the rare case of subjects receiving a regimen different from assignment, a per-protocol analysis will be performed as a secondary analysis, which will include subjects according to the product they actually receive in the study.

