7.3 MISSED VISITS AND LOST TO FOLLOW-UP

If a participant misses 1 visit after D28 or 2 visits after D28 that are not sequential, these will not be considered protocol deviations. However, 2 missed visits in a row or a total of 3 or more missed visits (regardless of whether or not they are sequential) over the duration of the study will be considered protocol deviations.

A subject will be considered lost to follow-up if he or she fails to return for 3 consecutive scheduled visits and is unable to be contacted by the study site staff.

The following actions must be taken if a subject fails to return to the clinic for a required study visit:

- The site will attempt to contact the subject and reschedule the missed visit within 7 days, counsel the subject on the importance of maintaining the assigned visit schedule, and ascertain if the subject wishes to and/or should continue in the study. If a missed visit cannot be rescheduled, the participant may continue with the next scheduled visit.
- Before a subject is deemed lost to follow-up, the investigator or designee will make every effort to regain contact with the subject (where possible, 3 telephone calls or home visits). These contact attempts should be documented in the subject's medical record or study file.
- Should the subject continue to be unreachable, he or she will be considered to have withdrawn from the study with a primary reason of lost to follow-up.

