8.4.3.2 Replacement of Withdrawn Subjects or Subjects Who Discontinue Study Agent

Subjects withdrawn prior to study agent administration will be replaced.

All subjects exposed to study agents MUST be included in the safety dataset.

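### The primary safety analysis groups misdosed participants by assigned arm, and the secondary analysis by product received is labelled per-protocol, which contradicts section 9.3

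*Combined protocol and SAP*

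**What the plan says.** Section 9.4.5 sets the primary safety population: "Safety analysis will be primarily MITT where individuals who receive assignment but do not receive any product are excluded". Section 9.3 says how that population is grouped. The MITT set "will include all randomized subjects that receive the study intervention and will be analyzed according to the initial randomization assignment".

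Section 9.4.5 then deals with misdosing. "In the rare case of subjects receiving a regimen different from assignment", it says, "a per-protocol analysis will be performed as a secondary analysis, which will include subjects according to the product they actually receive".

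Section 9.3 defines the per-protocol set differently, as randomized participants who "receive the study intervention consistent with the initial randomization assignment and complete the scheduled visits", analysed by assignment. In the same bullet, if anyone receives an intervention other than the assigned one, "an as-treated analysis will additionally be performed according to the actual intervention received".

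Section 8.4.3.2 adds a general rule: "All subjects exposed to study agents MUST be included in the safety dataset".

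**The concern.** Safety is one of the two primary objectives. Its endpoint is the incidence and severity of adverse events within 7 days of dosing (sections 3 and 9.1). Section 9.4.5 also compares the arms on solicited adverse events, related adverse events and serious adverse events.

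Grouping by assignment protects a randomized efficacy comparison. For safety it has a cost. If a participant assigned to placebo is given L9LS and reacts, the reaction counts as a placebo event; a participant assigned to L9LS who is given saline dilutes the L9LS rate. With one misdosed participant in each direction and a higher event rate on L9LS, the expected difference between arms shrinks.

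The analysis that would correct this carries a name that section 9.3 has already given to a different population. An analyst who follows both sections cannot tell from the label alone whether misdosed participants are moved to the other group or removed. That should be settled before unblinding, because a choice made afterwards could depend on the data.

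**Working it through.** **The definitions side by side**

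| Analysis | Who is in | Grouped by | Misdosed participants |
|---|---|---|---|
| MITT (9.3; primary for safety in 9.4.5) | All randomized and dosed | Assignment | Counted under the product not received |
| Per-protocol (9.3) | Correctly dosed completers | Assignment | Excluded |
| As-treated (9.3) | Added when misdosing occurs | Product received | Counted under the product received |
| Per-protocol (9.4.5; secondary) | No visit-completion condition stated | Product received | Counted under the product received |

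The last row matches the third row in substance and contradicts the second. So section 9.4.5 describes an as-treated analysis under the per-protocol name. MITT and an analysis of all dosed participants by product received contain the same people; only the grouping differs. Both can satisfy section 8.4.3.2, whereas the section 9.3 per-protocol set cannot once an exposed participant is misdosed or fails to complete visits.

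**The plan's nearest figure.** The documents give no misdosing rate and no figure for its effect. The nearest safety figure is in section 9.2.1: over a 90% chance of at least one event among 72 at a true rate of 0.032. It reproduces: 1 − (1 − 0.032)^72 = 0.904. It is not in dispute.

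**Ceiling for one misdosed participant.** Inputs: 216 assigned to L9LS and 72 to placebo (section 1.1 and Table 1). Let x of the 72 placebo-assigned participants have an event, and let one of the 72 have received L9LS.

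- By assignment, the placebo proportion is x/72.
- By product received, it is (x − 1)/71 if the misdosed participant had an event, and x/71 if not.
- The gap is (72 − x)/(72 × 71) in the first case, largest at x = 1: 71/5,112 = 1/72 = 1.4 points. In the second case its size is x/5,112, largest at x = 71, which is again 1/72.
- For one L9LS-assigned participant given placebo, the same algebra with 73 in the placebo group gives at most 1/73, also 1.4 points.
- The L9LS proportion moves by at most 1/216 = 0.5 points.

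**Expected size under assumed event rates.** The documents give no adverse event rates, so these are illustrations. With true rates p1 on L9LS and p0 on placebo:

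- One placebo-assigned participant given L9LS shifts the expected placebo proportion by (p1 − p0)/72. At 30% and 10% this is 0.20/72 = 0.3 points.
- With k participants misdosed in each direction, the expected by-assignment difference is (p1 − p0) × (1 − k/216 − k/72) = (p1 − p0) × (1 − k/54).

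| k each way | True difference 20.0 points (30% vs 10%) | True difference 40.0 points (50% vs 10%) |
|---|---|---|
| 0 | 20.0 | 40.0 |
| 1 | 19.6 | 39.3 |
| 2 | 19.3 | 38.5 |
| 4 | 18.5 | 37.0 |

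**The case against.** The strongest reply is that this is mainly a labelling slip. Section 9.4.5 says in its own words what its secondary analysis is, and analysis by product received is foreseen in both sections. The plan calls misdosing rare, and there is a single dosing session. Individual listings will show severity and relationship to study product (sections 9.4.5 and 9.4.10), and a significant error in administration is among the reportable problems in section 8.4.1. All of this stands, and it limits the size of the problem. It does not change the grouping of the primary analysis or remove the contradiction between the two sections.

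A reader might infer something stronger: that the safety analysis would lose everyone who withdrew or missed a visit, including those whose missed visits section 7.3 tolerates ("If a participant misses 1 visit after D28 or 2 visits after D28 that are not sequential, these will not be considered protocol deviations"). The documents do not support that. The section 9.4.5 analysis has no visit-completion condition. The section 9.3 per-protocol set excludes the misdosed, so it cannot be the analysis that section 9.4.5 describes. Section 8.4.3.2 also keeps every exposed participant in the safety dataset. Nor does the plan say whether a single missed visit would disqualify anyone under section 9.3, and it gives no per-visit miss rate from which a loss could be calculated.

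A reader might also conclude that the section 9.3 per-protocol set needs rewriting. Section 9.4.4 makes the efficacy analyses MITT, and the only analysis that names per-protocol is the mislabelled one in section 9.4.5. Correcting the label there is enough.

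**Conclusion.** The point holds in two parts. First, the primary safety analysis attributes a misdosed participant's adverse events to the assigned product, with analysis by product received only secondary. Second, that secondary analysis is called per-protocol, against the section 9.3 definition and against section 9.3's own term, as-treated.

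The practical effect is nil without misdosing. With it, one participant moves the placebo proportion by at most 1.4 points. One to four misdosed participants in each direction would shrink an assumed 20-point difference by 0.4 to 1.5 points in expectation. The ceiling rests only on the planned arm sizes; the other figures rest on the assumed event rates and numbers misdosed. The case for change is that the rule for a foreseen event should be clear and should suit a safety question. No large bias is claimed.

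**What to change.** Change section 9.4.5 only:

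- Make the primary safety analysis all participants who received study agent, grouped by the product actually received.
- Keep the by-assignment (MITT) analysis of the same participants as the check.
- Replace per-protocol with as-treated, so that the term agrees with section 9.3.

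Section 9.3 and the MITT efficacy analyses in section 9.4.4 stay as they are.

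The cost is a few lines of text, best settled before unblinding. The information needed is already recorded: the pharmacist keeps arm codes and accountability records (section 6.2.1), and staff document administration (section 6.4). If nobody is misdosed, the two groupings coincide and the primary safety result is unchanged.
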